9.5 Data Analyses

In Aims 1 and 2a, our focus will be on descriptive statistics (counts and proportions). In Aim 2b, the primary analyses will rely on intention-to-treat analysis to present the comparative results of the trial. All events following randomization will be counted. Analyses using post-randomization data (eg, intervention compliance) will be discussed as secondary analyses. We will distinguish non-compliance with intervention from non-compliance with follow-up (ie, missing data).

For our primary outcome measure, pMRCI, we will first perform correlation analyses between chronic medication count and pMRCI scores at baseline. We will analyze changes in pMRCI before and after intervention and evaluate the impact of intervention assignment on the change scores using linear regression. The cluster by health system effect will be accounted for in the calculation of robust standard errors. Given the pilot nature of this trial, we will focus on estimates of precision in detecting treatment effects that will aid in the planning of a larger, sufficiently powered ePCT. We will also explore treatment effects by gender, age strata and race/ethnicity, again focusing on estimates of with-stratum variabilities instead of statistical significance. We will use multiple imputation to account for missing data.

For our secondary outcome measure, FCMAHS, we will first construct summary scores of the FCMAHS subscales using principal components analysis. We will then analyze changes in FCMAHS before and after intervention and evaluate the impact of intervention assignment on the change scores using linear regression.

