1.2 Secondary Objectives

To determine the feasibility of the primary and secondary outcome measures for the subsequent ePCT:

a) To determine the feasibility of measuring the primary outcome, the patient-level Medication Regimen Complexity Index (pMRCI)¹⁻⁴, within the existing EHR systems, and to compare it with a more pragmatic measure, chronic medication count, as the primary outcome measure for the ePCT.

b) To determine the feasibility of measuring the secondary outcome, the Family Caregiver Medication Administration Hassles Scale (FCMAHS)⁵, a caregiver-reported outcome measure.

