6.1 Schedule of Evaluations

Assessment	Identify eligible population	Baseline: scheduling phone call (Day 0 + 28 days)	3 months post enrollment (Day 90 + 45 days)
Inclusion/Exclusion Criteria	X		
Patient demographics and diagnoses	X		
Care partner demographics		X	
Chronic medication count		X	X
Patient-level Medication Regimen Complexity Index (pMRCI)		X	X
Family Caregiver Medication Administration Hassles Scale (FCMAHS)		X	X

Feasibility measures			
Proportion of dyads that opt out	X		
Proportion of participants with data elements available to calculate pMRCI			·
		Throughout	intervention
Response rate and completion time for FCMAHS		Х	X
Proportion of pharmacist messages to PCP that receive			
acknowledgement or response		Throughout	intervention
Number of contacts between		Inoughout	
pharmacist and PCP and between pharmacist and dyad			
		Throughout	intervention
Time required by pharmacist to complete intervention			X
Type of recommendations made by pharmacist, acceptance rates for recommendations			X
Fidelity measures			
Proportion of intervention elements successfully completed by pharmacist			X

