9.4 Outcomes

Aim 1 is to assess the feasibility and acceptability of ALIGN in two different health care systems, to guide the subsequent evaluation of the effectiveness of the intervention in an embedded pragmatic trial. Data to measure feasibility will be acquired from the EHR, REDCap surveys completed by the pharmacists, and audiorecordings of pharmacist phone calls with care partners. We will collect the following measures:

- Proportion of dyads that opt out of the intervention;
- Proportion of pharmacist messages to the PCP that receive an acknowledgement or response;
- Number of contacts between pharmacist and PCP and between pharmacist and dyad;
- Time required by the pharmacist to complete the intervention;

Proportion of intervention elements, including pharmacist phone calls, successfully completed.
To evaluate intervention acceptability, we will track the following:

• Type of recommendations made by the pharmacist and acceptance rates for those recommendations (project assistants will review the EHR for notation of patient/care partner and PCP acceptance). The pharmacists will document each phone call with the dyad in the EHR and will record whether the patient and care partner have agreed to the recommendations. The template for the pharmacist message to the PCP (attached) includes a routing comment that asks the PCP to respond via secure chat or staff message – either to indicate acceptance or ask questions about the recommendations.

Aim 2 is to determine the feasibility of the primary and secondary outcome measures for the subsequent ePCT:

Aim 2a is to determine the feasibility of measuring the primary outcome, the patient-level Medication Regimen Complexity Index (pMRCI)¹⁻⁴, within the existing EHR systems, and to compare it with a more pragmatic measure, chronic medication count, as the primary outcome measure for the ePCT.

Aim 2b is to determine the feasibility of measuring the secondary outcome, the Family Caregiver Medication Administration Hassles Scale (FCMAHS)⁵, a caregiver-reported outcome measure.

As described in Section 6.2, we will develop the procedures for collecting the pMRCI and FCMAHS. In Aim 2a, feasibility will be measured as follows:

• Proportion of participants with data elements available vs. unavailable to calculate the pMRCI.

To compare it with chronic medication count as the primary outcome measure for the ePCT, we will measure:

- Change in chronic medication count; and

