- Change in pMRCI from baseline to 3 months.

Chronic medication count will be obtained from the EHR using algorithms refined in OPTIMIZE.

In Aim 2b, feasibility will be measured as follows:

- Response rate and completion time for the FCMAHS using each mode of administration.
- Change in FCMAHS from baseline to 3 months.

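### Change in chronic medication count is collected for the Aim 2a comparison with pMRCI, but section 9.5 fits an arm model to pMRCI only and links the two measures only by a baseline correlation

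*Combined protocol and SAP*

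**What the plan says.** Section 1.2 sets out, besides testing the feasibility of pMRCI, "to compare it with a more pragmatic measure, chronic medication count, as the primary outcome measure for the ePCT". Section 9.4, like section 3, turns this into measurements. Under the lead-in "To compare it with chronic medication count as the primary outcome measure for the ePCT, we will measure" it lists "Change in chronic medication count; and" and "Change in pMRCI from baseline to 3 months". The schedule in section 6.1 has both measures at baseline and at 3 months.

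Section 9.5, which repeats section 9.1, opens with a general statement: "In Aims 1 and 2a, our focus will be on descriptive statistics (counts and proportions". For pMRCI it then says "we will first perform correlation analyses between chronic medication count and pMRCI scores at baseline", followed by a linear regression of change in pMRCI on intervention assignment. FCMAHS also gets a regression of change on assignment. Chronic medication count gets none. No baseline covariate is stated for any of these models.

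On data completeness, the Aim 2a feasibility measure in section 9.4 is "Proportion of participants with data elements available vs. unavailable to calculate the pMRCI". There is no matching item for the count, although section 6.2 says that ways of identifying chronic medications in the Johns Hopkins EHR are still being examined.

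**The concern.** Comparing two candidate primary outcomes for a trial means asking which one moves under the intervention, how precisely, and how reliably it can be obtained. The only analysis in section 9.5 that involves both measures is cross-sectional and made before any pharmacist contact, so it carries no information about response. The analysis that does bear on response is specified for one candidate only.

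Two things are at stake. First, section 9.5 says that the pilot estimates should help to plan a sufficiently powered ePCT, yet no effect or variance estimate is specified for one of the two outcomes it might use. Second, section 2.1 faults earlier work for looking at drug classes or drug numbers and leaving out dosing schedule and directions for use. A count cannot register a simpler schedule; pMRCI can. If a high baseline correlation were taken as evidence that the two are interchangeable, that distinction would be lost.

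**Working it through.** **1. The plan's own precision figure.** Section 9.2 gives 30 dyads per arm, 10% attrition, SD = 1 and an interval width of 0.4 SD. Evaluable per arm: 30 × 0.9 = 27. The half-width for one arm's mean is t(0.975, 26)/√27 = 0.396. So the 0.4 reproduces as a one-arm half-width. It is not the precision of an arm difference, which this comparison needs.

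**2. Precision of an arm difference.** Half-width = t(0.975, 52) × √(2/27) = 0.546 SD (0.533 with the normal quantile). This applies to either measure in units of its own SD. It ignores clustering by health system and the uncertainty in the SD itself.

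**3. Why the baseline correlation is high by construction.** Section 6.2 describes pMRCI as weighted values of regimen components, so more drugs give a higher score. Assume a count K with mean 9 and SD 3, and independent per-drug weights with mean 2.5 and SD 1.2. None of these values is in the documents.
- Variance of pMRCI from K: 2.5² × 3² = 56.25.
- Variance from the weights: 9 × 1.2² = 12.96.
- Correlation = √(56.25 / (56.25 + 12.96)) = √(56.25 / 69.21) = 0.90.

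Over a wider range of assumed inputs, simulation gave 0.68 to 0.96. Nothing about the intervention enters this calculation.

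**4. Baseline correlation against change correlation.** Baseline pairs were simulated with correlation 0.80, and changes were drawn separately with correlation 0, 0.5 or 0.9. The baseline correlation was 0.80 each time; the change correlations came out at 0.00, 0.50 and 0.90. The first does not determine the second.

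**5. What the choice of outcome can do to the ePCT.** n per arm = 2(1.96 + 0.84)²/d², for individual randomisation, 80% power and two-sided alpha 0.05 (all assumed), before cluster inflation.

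| Standardised effect d | n per arm |
|---|---|
| 0.2 | 393 |
| 0.3 | 175 |
| 0.4 | 99 |

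The ratio of sample sizes for two outcomes is the squared inverse ratio of their standardised effects. An illustrative simulation with the inputs of step 3 gave these sizes for the count relative to pMRCI:
- effect all from stopping drugs: (0.70/0.79)² = 0.79;
- mixed stopping and simplification: (0.84/0.54)² = 2.4;
- mostly simplification: (0.82/0.17)² = about 23.

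The scenarios are assumptions. They show only that either measure could come out ahead.

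**6. How well 27 per arm can separate the two effects.** With correlation ρ between the change scores, the half-width for the difference of two standardised effects in the same patients is 1.96 × √(2/27) × √(2(1 − ρ)). For assumed ρ of 0.5, 0.7 and 0.9 this is 0.53, 0.41 and 0.24 SD.

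**The case against.** The strongest reply is that the plan already declares change as the basis of comparison. Sections 3 and 9.4 name it for both measures, and section 9.5 calls the baseline correlation a first step. This stands. A reader might infer that baseline correlation is the plan's only means of comparison, but the documents do not say so. What they lack is any stated analysis of the change in count, or of the two changes together.

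A reader might also infer that Aim 2a is confined to counts and proportions, or that it cannot be answered at all. The text states a focus, not a limit, and a by-arm summary of change in count would be compatible with it. Nor does the text say that the pilot must choose: the word is compare, although informing a choice is the evident purpose. No rule says that a high correlation would lead the team to adopt the count.

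A further tempting reading is that the count would be the costlier outcome, perhaps by a factor above 20. The documents give no drug counts, weights, change SDs or split between stopping and simplifying. The pharmacist's output is described as deprescribing recommendations, and in the stop-only illustration the count is the more efficient measure.

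Finally, a pilot of this size ranks outcomes poorly. The illustrative gap in the stop-only scenario (0.79 − 0.70 = 0.09) lies inside all three half-widths of step 6, and the mixed gap (0.84 − 0.54 = 0.30) lies inside two of them. This limits how much weight the comparison can carry. It does not justify leaving one candidate without an estimate.

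**Conclusion.** The point holds as a gap between sections 3 and 9.4, which collect change in both measures for this comparison, and section 9.5, which specifies an arm-level analysis for only one of them. The sole stated joint analysis cannot show responsiveness. That conclusion follows from its timing and from how pMRCI is built, and it does not depend on the assumed 0.90.

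The effect on the ePCT could be material, for example 393 against 175 per arm if the standardised effects were 0.2 and 0.3. Its direction and size are unknown from the documents. The gap should be closed before analysis; it does not undermine the pilot's feasibility aims.

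**What to change.** In sections 9.1 and 9.5:
- Fit an identical arm model to pMRCI and to chronic medication count, with the same handling of health system and missing data. Add the baseline value of each outcome as a covariate. The current text states none, so this also modifies the pMRCI model.
- For each measure report the arm difference, residual SD, standardised effect (difference / residual SD) with 95% interval, and the proportion computable from the EHR. Eligibility already requires at least 5 chronic medications, so the count's completeness at 3 months is the more informative figure.
- Report the correlation of the two change scores.
- State that these results, together with feasibility, inform the ePCT choice, and that the baseline correlation is descriptive only.
- State the expected precision: a 95% half-width of about 0.55 SD for each standardised effect with about 27 evaluable per arm. The result should be presented as informing the choice, not deciding it.

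The cost is one extra regression, one extra correlation, a baseline covariate in the pMRCI model and a completeness tally for the count. All of it uses data already scheduled, with no added patients or visits.

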The proposed pragmatic intervention consists of the following strategies: 1) direct-toconsumer deprescribing educational materials designed to activate the care partner and PLWD; 2) a telehealth visit in which a clinical pharmacist discusses benefits and harms of the patient's medications with the patient and care partner in the context of their goals and preferences; and 3) pharmacist-PCP communication in which the pharmacist provides tailored deprescribing recommendations designed to be useful and actionable for the PCP. The study will assess the feasibility and preliminary efficacy of the intervention in two healthcare systems, to guide the subsequent evaluation of the intervention in an ePCT.

We will enroll 60 patients and their care partners as dyads (15 dyads per arm at each site). Patient eligibility criteria will be: age \geq 65 years with a diagnosis of ADRD from ICD-9 or ICD-10 visit codes or from the EHR problem list and \geq 5 chronic medications. In

Baltimore, the study site will be 1-4 clinics that are part of Johns Hopkins Community Physicians (JHCP). In Denver, the study sites will be KPCO greater Denver metro primary care practices. Dyads at each pilot site will be randomly assigned to receive the pharmacistled intervention immediately after the educational mailing or to a delayed intervention control group that will receive the pharmacist-led component 3 months after the mailing. (Please see the Consent section for a discussion of consent options for consenting patients as part of pragmatic trials.)

This protocol employs a pragmatic design. The intervention is delivered by clinical pharmacists who are already integrated in primary care clinics at JHCP and KPCO. The pharmacists are trained in complex geriatric medication management and routinely provide comprehensive medication management to Medicare beneficiaries.

Aim 1 is to assess the feasibility and acceptability of ALIGN in two different health care systems, to guide the subsequent evaluation of the effectiveness of the intervention in an ePCT. Data to measure feasibility will be acquired from the EHR, checklists completed by the pharmacists, and audiorecordings of pharmacist phone calls with care partners. We will collect the following measures:

• Proportion of dyads that opt out of the intervention;

• Proportion of pharmacist messages to the PCP that receive an acknowledgement or response;

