9 STATISTICAL CONSIDERATIONS

9.1 General Design Issues

This is a pilot of a future pragmatic, cluster randomized trial. The pilot aims to assess feasibility and acceptability of the intervention. There are no statistical hypotheses. Our conceptual hypotheses are that the pilot intervention will be acceptable to patients and clinicians and feasible to conduct. In Aims 1 and 2a, our focus will be on descriptive statistics (counts and proportions). In Aim 2b, the primary analyses will rely on intention-to-treat analysis to present the comparative results of the trial. All events following randomization will be counted. Analyses using post-randomization data (eg, intervention compliance) will be discussed as secondary analyses. We will distinguish non-compliance with intervention from non-compliance with follow-up (ie, missing data).

For our primary outcome measure, pMRCI, we will first perform correlation analyses between chronic medication count and pMRCI scores at baseline. We will analyze changes in pMRCI before and after intervention and evaluate the impact of intervention assignment on the change scores using linear regression. The cluster by health system effect will be accounted for in the calculation of robust standard errors. Given the pilot nature of this trial, we will focus on estimates of precision in detecting treatment effects that will aid in the planning of a larger, sufficiently powered ePCT. We will also explore treatment effects by gender, age strata and race/ethnicity, again focusing on estimates of with-stratum variabilities instead of statistical significance. We will use multiple imputation to account for missing data.

For our secondary outcome measure, FCMAHS, we will first construct summary scores of the FCMAHS subscales using principal components analysis. We will then analyze changes in FCMAHS before and after intervention and evaluate the impact of intervention assignment on the change scores using linear regression.

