9.2 Sample Size and Randomization

Sample size calculation: With an attrition rate of 10%, a sample size of 30 dyads per arm will produce a 2-sided 95% confidence interval with a width equal to 0.4 standard deviation (SD) when the SD of the study outcome (ie, based on normalized score) is 1.

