9.2.1 Treatment Assignment Procedures

Enrolled dyads will be randomized prior to the scheduling phone call using computer-generated random numbers to either the intervention group or the delayed intervention group. The intervention group will then be scheduled to have the pharmacist telehealth visit immediately (within 4 weeks) after enrollment. The delayed intervention group will be scheduled to receive the pharmacist-led component 3-4 months after enrollment. For dyads randomized to the delayed group, the project assistant will say, "I will call you in about 3 months to remind you of your appointment with the pharmacist." Due to the nature of the intervention, participants, pharmacists and PCPs cannot be masked. Project assistants will enter data into a REDCap database so that the researchers can analyze it without having access to group assignment.

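### The arm comparison on pMRCI and FCMAHS uses change scores with no baseline covariate named; adding the baseline value would usually narrow the intervals at almost no cost

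*Combined protocol and SAP*

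**What the plan says.** Section 9.5 takes the changes in pMRCI, and then in FCMAHS, and will "evaluate the impact of intervention assignment on the change scores using linear regression". Section 9.1 carries the same text. For pMRCI it adds robust standard errors for health system, exploration by gender, age and race/ethnicity, and multiple imputation. Neither section names the baseline value, or any other covariate, as a model term.

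The purpose is given in the same paragraph: "we will focus on estimates of precision in detecting treatment effects", as input to planning the larger ePCT. Section 9.1 also states that the pilot has no statistical hypotheses.

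The schedule in Section 6.1 places pMRCI, chronic medication count and FCMAHS at baseline and at 3 months. Section 9.2.1 assigns dyads "using computer-generated random numbers to either the intervention group or the delayed intervention group"; no balancing on baseline scores is described.

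**The concern.** A change score fixes the slope of the 3-month value on the baseline value at 1. Unless that slope really is near 1, part of any chance baseline difference between the arms passes into the estimated effect, and the interval is wider than it needs to be. Including the baseline value lets the data estimate the slope.

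In this pilot the product of the comparative analysis is a set of precision estimates, so the choice of model bears directly on that product. If the ePCT were to adjust for baseline, a change-score variance carried into its planning would be too large. Aim 2a also weighs pMRCI against chronic medication count as the ePCT primary outcome by looking at change in each. The penalty from using change depends on each measure's own stability, so it need not be the same for both.

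**Working it through.** **Inputs.** 30 dyads per arm, 10% attrition, 2-sided 95% interval and SD 1 (Section 9.2); "15 dyads per arm at each site" (Section 3), hence 1:1 allocation. Analysed: n = 30 × 0.9 = 27 per arm, N = 54. The baseline to 3-month correlation, rho, is not in the documents, so I vary it from 0.3 to 0.98. The only correlation planned in 9.1 and 9.5 is a different one, between medication count and pMRCI at baseline. I also assume SD 1 at both times, the same rho in both arms, and ordinary standard errors rather than the plan's robust ones.

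**The plan's own figure.** Section 9.2 gives an interval width of 0.4 SD, "when the SD of the study outcome (ie, based on normalized score) is 1". This reproduces as the t half-width of one arm's mean: t(0.975, 26)/√27 = 0.396. For the arm difference at SD 1 the half-width is t(0.975, 52) × √(2/27) = 0.546 and the full width 1.092. That mismatch is a separate matter, but it means that 0.4 cannot serve as the reference width for the arm effect.

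**Variance of the arm difference.**
- Change score: 2(1 − rho) × 2/n, with t on 52 df.
- Baseline-adjusted: (1 − rho²) × (2/n) × (1 + 1/(N − 4)), with t on 51 df. The last factor, 1.02, is the price of estimating the slope.

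At rho = 0.7:
- Change score: SE = √(0.60 × 2/27) = 0.211, full width 2 × 2.007 × 0.211 = 0.846 (unrounded inputs).
- Adjusted: SE = √(0.51 × 2/27 × 1.02) = 0.196, full width 2 × 2.008 × 0.196 = 0.788.
- Ratio: 0.846/0.788 = 1.07.

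**Carried imbalance.** Given an observed baseline difference d, the expected change-score estimate is the true effect minus (1 − rho)d. The SE of d is √(2/27) = 0.272 SD. The last column is the size of the shift at d = 0.272.

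| rho (assumed) | Width, change score | Width, adjusted | Change score wider by | Shift at 1-SE imbalance |
|---|---|---|---|---|
| 0.3 | 1.292 | 1.053 | 23% | 0.191 |
| 0.5 | 1.092 | 0.956 | 14% | 0.136 |
| 0.7 | 0.846 | 0.788 | 7% | 0.082 |
| 0.8 | 0.691 | 0.662 | 4% | 0.054 |
| 0.9 | 0.488 | 0.481 | 1.5% | 0.027 |
| 0.95 | 0.345 | 0.345 | 0.2% | 0.014 |
| 0.98 | 0.218 | 0.220 | −0.5% | 0.005 |

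The two widths are equal at rho = 0.959. Beyond that the adjusted interval is very slightly wider.

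**One effect, not two.** Apart from the small-sample factor, the excess variance per unit is 2(1 − rho) − (1 − rho²) = (1 − rho)². That is the variance of the carried imbalance (1 − rho)d, so the last two columns describe the same loss.

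**Simulation.** 10,000 trials with no true effect were run at each of rho = 0.5, 0.7 and 0.9. The slopes of the change-score estimate on the imbalance were −0.49, −0.30 and −0.10; for the adjusted model they were about 0. The mean estimate over randomizations was about 0 under both models.

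**Planning.** In large samples the variance ratio is 2/(1 + rho): 1.33, 1.18 and 1.05 at rho = 0.5, 0.7 and 0.9. That is the factor by which a change-score variance would overstate the sample needed by a baseline-adjusted ePCT, before any allowance for clustering.

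**The case against.** **Silence on covariates.** A reader might infer that the plan commits to an unadjusted model. It does not say so. Change regressed on assignment plus baseline would also fit the stated sentence. What stands is that no baseline term is named, so the model has to be settled in the text.

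**Bias.** A reader might infer that change scores give a biased effect. Over randomization they do not. The shift arises only given the imbalance actually observed, and the change-score interval already allows for it.

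**High stability of pMRCI.** Patients take at least 5 chronic medications, follow-up is 3 months, and controls receive only the mailing before then. If rho is 0.9 or more, the gain is 1.5% or less. This objection stands: a material gain for pMRCI is not established.

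**Limited consequence.** This is a feasibility pilot with a descriptive focus for Aims 1 and 2a, and no stated decision rule uses the arm estimate. The documents do not say that the ePCT will adjust for baseline; if it analyses change, the change-score SD is the right input. If it does adjust, the error is conservative, and rho can be recovered from the same data. All this limits the importance of the point. It does not remove it, because precision for planning is the declared output.

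**FCMAHS baseline.** Under Section 6.2.2 randomization precedes the enrollment call, and the scale is offered after the consult has been scheduled, to care partners who cannot be masked. Section 4.3 also allows a later e-mailed link. The baseline is therefore not strictly pre-randomization. That weakens it as a covariate, but it affects the change score too.

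**Conclusion.** The point holds as a free improvement, not as an error that invalidates the analysis. As written, the regression names no baseline term. With 27 analysed per arm, the resulting interval is about 14% wider than the adjusted one at rho 0.5, 7% at 0.7, 4% at 0.8, 1.5% at 0.9 and essentially equal at 0.95. The size rests on an assumed rho, on equal SDs at the two times and on complete data for 27 dyads per arm. FCMAHS is optional for care partners, so its analysed number may be lower and its chance imbalance larger. For pMRCI the benefit may be slight.

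**What to change.** In Sections 9.1 and 9.5, state that the 3-month value (or, equivalently for the arm effect, the change) is regressed on assignment plus the baseline value of the same measure. Define that baseline as one recorded before the pharmacist visit, and acknowledge that baseline FCMAHS is taken after randomization.

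For pMRCI, FCMAHS and chronic medication count, report rho, the change-score SD and the adjusted residual SD. The ePCT can then be planned under either analysis, and the Aim 2a comparison of the two medication measures does not depend on change scores alone. A health-system term is optional and is not needed for this point.

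The cost is a sentence or two of text and about one degree of freedom, with no new data. If rho exceeds about 0.96 the loss of precision is negligible (0.220 against 0.218 SD at rho 0.98).

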The eligible patient population for the pilot study will be all patients at the two pilot clinics who are age 65 or greater with a diagnosis of Alzheimer's disease and related dementias (ADRD) from either ICD visit codes or documentation on the problem list. Patients must also be taking 5 or more chronic medications, and active patients, defined as having ≥ 1 visit to the primary care clinic within the past year. We will enroll 60 patient-care partner dyads (15 dyads per arm at each site).

STUDY TEAM ROSTER

Principal Investigator:	[name], MPH, PhD Johns Hopkins University School of Medicine [name] [contact] [contact] [contact]
Co-Investigators:	[name], MS Institute for Health Research, Kaiser Permanente Colorado [name] [contact] [contact] [contact] Site Principal Investigator, Kaiser Permanente
	[name], MPH Johns Hopkins University School of Medicine [name] [contact] [contact] [contact] Co-Investigator
	[name] Johns Hopkins Bloomberg School of Public Health [name] [contact] [contact] [contact] Co-Investigator
	[name] Johns Hopkins Center on Aging and Health [name] [contact] [contact] [contact] Co-Investigator, Statistician
	[name], MSPH Institute for Health Research, Kaiser Permanente Colorado

[name] [contact] [contact] [contact] Co-Investigator

PARTICIPATING STUDY SITES

[name], MPH, PhD

Johns Hopkins University School of Medicine [name] [contact] [contact] [contact]

[name], MS

Institute for Health Research, Kaiser Permanente Colorado [name] [contact] [contact] [contact]

1 STUDY OBJECTIVES

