1.1 Primary Objective

To assess the feasibility and acceptability of ALIGN in two different health care systems, to guide the subsequent evaluation of the effectiveness of the intervention in an embedded pragmatic trial (ePCT).

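### The pMRCI standard error is clustered on health system, but with only two systems it rests on one degree of freedom and is too noisy to plan the ePCT

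*Combined protocol and SAP*

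**What the plan says.** Sections 9.1 and 9.5 carry the same pMRCI paragraph. The plan will "evaluate the impact of intervention assignment on the change scores using linear regression", and then: "The cluster by health system effect will be accounted for in the calculation of robust standard errors". No health-system term is named in the model. No reference distribution, degrees of freedom or small-cluster correction is given. The next sentence gives the purpose: "we will focus on estimates of precision in detecting treatment effects that will aid in the planning of a larger, sufficiently powered ePCT".

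The design is set out elsewhere. Section 1.1 aims to "assess the feasibility and acceptability of ALIGN in two different health care systems", so there are two clusters. Section 3 states: "Dyads at each pilot site will be randomly assigned to receive" the pharmacist component at once or after a delay, so the dyad is the randomised unit and both arms exist in each system. The Précis and Section 3 plan 60 dyads, fifteen in each arm at each site. Section 9.2 begins its calculation "With an attrition rate of 10%, a sample size of 30 dyads per arm" and takes the outcome SD as 1.

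The FCMAHS paragraph has no clustering sentence, so this point concerns pMRCI only.

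**The concern.** A cluster-robust variance estimates uncertainty from the variation between cluster totals, so it needs many clusters. Two clusters give a single contrast. The standard error then depends on how far apart the two within-system effects happen to fall. If they are close, it is near zero however much the dyads vary.

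Clustering on health system is also not required by the design. Dyads are allocated individually within system, so a difference in mean pMRCI change between systems is a stratum effect and belongs in the model.

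At stake is the standard error and confidence interval for the pMRCI effect, which the paragraph itself presents as an input to the larger trial.

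**Working it through.** **Inputs.** From the documents: 2 systems; 60 dyads, 15 per arm per system; 10% attrition, leaving 27 per arm and 54 in total; SD 1; two-sided 95% interval. Assumed: no true effect, complete data and, for the closed forms, arms split evenly over systems (13.5 per arm per system).

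**The plan's own precision figure.** Section 9.2 gives 30 per arm for a width of 0.4 SD. The smallest n with t(0.975, n−1)/√n ≤ 0.4 is 27 (0.396), and 27/0.9 = 30. The figure therefore reproduces, but as the half-width of an interval for one arm's mean. The between-arm half-width at 27 per arm is about 0.55 SD, and that is the benchmark here.

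**Why there is 1 df.** Least-squares scores sum to zero over the sample. With two clusters the two score vectors are equal and opposite, so the middle matrix of the sandwich has rank 1. It had rank 1 in every one of 10,000 simulated trials per scenario.

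Let d₁ and d₂ be the within-system arm differences. With balanced arms:

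- estimate = (d₁ + d₂)/2
- clustered SE with the G/(G−1) factor = |d₁ − d₂|/2
- without the factor, this is divided by √2.

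A numerical check of the second line gave 0.2358 on both sides.

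**True SE.** √(2/27) = 0.272 SD.

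**Spread of the clustered SE.** With the factor, SE/0.272 is distributed as |Z|, Z standard normal.

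- 10th percentile: 0.1257 × 0.272 = 0.034. 90th percentile: 1.645 × 0.272 = 0.447. The ratio is about 13.
- Squared: 0.1257² = 2% and 1.645² = 271% of the true variance.
- P(|Z| < 0.5) + P(|Z| > 2) = 0.383 + 0.046 = 0.43, the chance of being wrong by more than a factor of two.

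**Coverage.** Estimate/SE follows t with 1 df, so:

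- 1.96 with factor: (2/π)·atan(1.96) = 70.0%
- 1.96 without factor: (2/π)·atan(1.96/√2) = 60.2%
- t(1) critical value 12.706: 95% with the factor, 92.9% without. Median half-width with the factor: 12.706 × 0.674 × 0.272 = 2.33 SD.

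**Simulation (8,000 to 20,000 trials per scenario).** Scenarios covered balanced and simple randomisation, with and without a difference in system means, and with system in or out of the model.

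| Method | Coverage | Half-width (SD) |
|---|---|---|
| Clustered, 1.96, with factor | about 70% (0.675 to 0.711) | median about 0.37 |
| Clustered, 1.96, no factor | about 60% (0.572 to 0.611) | smaller by √2 |
| Clustered, t(1) | 93 to 95% | median 2.3 to 2.4 with factor |
| System fixed effect, ordinary SE | 94.6 to 95.3% | 0.54 (0.48 to 0.61, 10th to 90th percentile) |
| System fixed effect, HC3 | 95.1 to 95.9% | median 0.56 to 0.57 |

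The closed form for the fixed-effect model is t(0.975, 51) × 0.272 = 0.546. Its variance estimate lies between 77% and 128% of the truth (10th to 90th percentile). Adding a system term while still clustering on system does not help: coverage with 1.96 was about 71%.

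If all 60 dyads had complete data, the clustered coverages stay at 60% and 70%, the t(1) median half-width is 2.2 SD and the fixed-effect half-width is 0.51 SD.

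**The case against.** **The sentence names no estimator.** A system covariate with heteroscedasticity-robust errors would avoid the problem. That reading is possible, but the text places the system effect in the standard-error calculation and names no system term. If a covariate was meant, the wording still needs changing.

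**This is a pilot.** Section 9.1 states no statistical hypotheses and makes Aims 1 and 2a mainly descriptive. No decision rule uses this interval. The ePCT will be cluster randomised, so its sample size needs outcome SDs and between-cluster variation more than this standard error. All of this stands and limits the severity. It does not rescue a standard error that the plan specifies and says it will use for planning.

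**The method is noisy rather than wrong on average.** With the factor and balanced arms, the squared standard error is unbiased, and t(1) gives valid coverage. Both are true. An interval with a median half-width of 2.3 SD is valid but too wide to use.

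**Multiple imputation was not simulated.** The figures are for complete data. Imputation adds its own variance but does not add clusters.

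**The replacement has limits.** It supports inference for these two systems only. If the effect varied between systems with an assumed SD of 0.3, it covers 95% for the average over these two but 88 to 89% for systems in general. Clustering with t(1) does cover that wider target, at a median half-width of about 3.0 SD. The replacement also treats dyads as independent within system, although pharmacists are shared, and the documents do not say how many take part. Under assumed pharmacist effects in the intervention arm, coverage with two per system is 94.6%, 93.1% and 91.2% at variances 0.02, 0.05 and 0.10. With one per system it is 91.5% and 87.9% at 0.05 and 0.10.

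**Conclusion.** The concern holds. As written, the pMRCI standard error has one degree of freedom. Its 95% interval covers 60 to 70% with a normal critical value or is too wide to use with t(1). The standard error itself is wrong by more than a factor of two in about 43% of trials. The 1-df result follows from having two clusters. The sizes assume 54 complete cases, normal residuals with SD 1, near-balanced arms and no effect difference between systems.

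The damage is confined to the standard error and interval for one effect. The point estimate, outcome SDs, baseline correlation with medication count and feasibility objective are untouched. It should be fixed before analysis, but it does not threaten the trial.

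**What to change.** In Sections 9.1 and 9.5, replace the clustering sentence for pMRCI with wording such as:

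> Change in pMRCI will be regressed on arm and health system (fixed effect), without clustering on health system. Standard errors will be [model-based / HC3: name one]. Dyads are treated as independent within system. Inference is conditional on these two systems; between-system variation in the effect cannot be estimated from two systems.

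Choose the standard error in advance; both options perform adequately here. Report the two system-specific effects descriptively, and describe results by clinic and pharmacist, because the independence assumption depends on how many pharmacists deliver the intervention.

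The cost is wording in two sections and one model degree of freedom. No new data are needed.

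Using the same model for FCMAHS or medication count is optional, as is adding baseline pMRCI as a covariate. Neither is needed to correct this point.
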